3.3 Conventions for missing data

Except in the cases specified, missing data will not be replaced.

3.4 Baseline definition

Baseline measurements will be the last measurement taken prior to inclusion or the last measurement taken prior to the first administration of treatment.

3.5 Statistics

The confidence intervals provided will be two-sided 95% confidence intervals except for the primary criterion where the calculated confidence interval will be a one-sided 95% confidence interval.

Quantitative data will be described using the following descriptive statistics: number, mean, standard deviation, median, first and third quartile, and minimum and maximum. These statistics will be considered the usual statistics for the analysis of quantitative variables. Quantitative variables may be categorized using their median or a cut-off known from the medical literature.

Categorical variables will be summarized using the following descriptive statistics: the number, frequencies and percentages for each level of the variable. These statistics will be considered the usual statistics for the analysis of categorical variables.

When necessary, the 95% confidence intervals for the proportions can be calculated from the exact binomial distribution.

Survival data will be estimated and plotted using the Kaplan Meier method (Kaplan and Meier., 1958). They will be described by the median and rates calculated at different time points with their two-sided 95% confidence intervals. Confidence intervals for the rates will be constructed from the Greenwood variance calculated using the log-log transformation.

Median follow-up time will be estimated using the inverse Kaplan-Meier method (Shemper, 1996).

As an exploratory measure, for uni and multivariate analyses, the hazard ratios will be estimated using a Cox model (Cox, 1984). The hypothesis of proportionality of the rates will be tested using the graphical representation and the test based on Schönfeld's residuals (Grambsch, 1994); the linearity of the effect of the continuous variables on the risk will be evaluated from the graphical representation of the martingale residuals. Confidence intervals for the coefficient estimates of the Cox models will be calculated using the Wald method.

4 Analyses statistiques

	ITT Population	ITTm Population	Population de tolérance
Baseline description			
Eligibility	X		
Demographics	X		
Clinical characteristics	X		
Biological characteristics	X		
Disease characteristics	X		
Main criterion			
Tumoral control	X		
Critères secondaires			
Follow-up time	X		
OS, PFS	X		
Tumoral control (Centralised review)	X		
Objective response	X		
Time to therapeutic failure	X		
Time to autonomy deterioration	X		
Time to QOL deterioration	X		
Safety			
Treatment			X
Toxicities			X

4.1 Baseline characteristics

4.1.1 Eligibility

Population : ITT

Patient eligibility at inclusion will be described by:

- The number and percentage of patients who met all inclusion criteria
- Number and percentage of patients who met all non-inclusion criteria
- Number and percentage of patients who met all inclusion and non-inclusion criteria

4.1.2 Demographics

Population : ITT

Following characteristics will be described :

- Age (years) ;
- Number of patients per center ;
- Sex

4.1.3 Clinical characteristics

Population : ITT

Following characteristics will be described :

- Weight (kg) ;
- ECOG (0 vs 1) ;
- Geriatric assessment (yes/no) before starting treatment
- ADL and IADL
- Köhne Score

Definition :

Low :

- OMS 0-1 and only one metastatic site

Intermediate :

- OMS 0-1 and more than one metastatic site and PAL \leq 300 U/L
- OMS >1 and white blood cells $\leq 10 \times 10^9/L$ and only one metastatic site

High :

- OMS 0-1 and more than one metastatic site and PAL > 300 U/L
- OMS >1 and white blood cells $> 10 \times 10^9/L$
- OMS >1 and white blood cells $\leq 10 \times 10^9/L$ and more than one metastatic site

4.1.4 Biological characteristics

- Haemoglobin (g/dL)
- Creatinin ($\mu\text{mol/L}$)
- PAL (U/L)
- Leucocytes ($/\text{mm}^3$)
- CEA ($\mu\text{g/L}$)

4.1.5 Disease characteristics

Population : ITT

Following characteristics will be described :

- Time between primary tumor diagnosis and study inclusion (months)
- Time between metastatic diagnosis and study inclusion (months)
- Primary tumor Localization
- Primary tumor resection
- Metastatic localization
- BRAF status
- RAS status
- MSI/MSS status
- Previous treatment and description

4.2 Follow-up

4.2.1 Definition

Population : ITT

Median follow-up time is defined as the time interval between the date of inclusion and the date of last news (patients alive or lost to follow-up) or the date of death (regardless of cause).

4.2.2 Evaluation

The median follow-up time (for alive patients) and its 95% confidence interval will be calculated in months. It will be estimated by the inverse Kaplan Meier method.

4.3 Main efficacy criterion

Population : ITTm

4.3.1 Definition

The primary endpoint is to evaluate the tumor control rate. It is defined as the percentage of patients with a complete, partial or stable tumor response 2 months after the start of treatment according to the investigator's RECIST v1.1 criteria.

Patients who stopped treatment (due to radiological progression or death) before 2 months after the start of treatment will be considered as having failed tumor control. Discontinuations for other causes will be reviewed on a case-by-case basis; verify that the patient has not taken any subsequent treatment between the date of discontinuation and the date of imaging. In case of clinical progression, if no imaging is available, the patient will be considered to have failed tumor control; otherwise, review the medical record to determine the reason for the clinical progression.

If imaging at 2 months is not available but imaging before 2 months is done then:

- Patients with radiological and/or clinical progression on a previous evaluation will be considered to have failed tumor control at 2 months.
- Patients who have died (regardless of cause) before 2 months will be considered to have failed tumor control.

If 2-month imaging is not available, subsequent imaging will be reviewed if available and the patient record will be reviewed.

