#### 2) Secondary criteria

The **secondary endpoints** are defined as follows:

- Overall treatment **tolerance** will be assessed by the rate of observed toxicities, graded according to NCI-CTC v4.

- **Overall survival is** defined as the time from the date of inclusion to the date of death from any cause. Patients lost to follow-up or alive at the time of analysis will be censored at the date of last report. A minimum follow-up of 1 year for the last included patient is required.

- **The tumor control rate** assessed in centralized review is defined as the percentage of patients with complete tumor response, partial tumor response, or tumor stability on regorafenib therapy 2 months after the start of therapy (RECIST criteria V1.1).

- **The objective response rate is** defined as the occurrence of at least one complete or partial response assessed from the best response (according to RECIST v1.1 criteria) during the treatment evaluations (Appendix 4). Patients who discontinue the study without response assessment will be considered non-responders.

- **Time to treatment failure is** defined as the time from the date of inclusion to the date of treatment discontinuation (regardless of cause) or death (regardless of cause). Living patients without treatment discontinuation will be censored at the date of last treatment administration.

- **Progression-free survival is** defined as the time from the date of inclusion to the date of first investigator-rated progression (clinical or radiological) or death (from any cause). Patients alive without progression will be censored at the date of last news. A minimum

follow-up of 1 year for the last included patient is required.

- **The regorafenib dose intensity** will be calculated during the first 2 cycles of treatment **and over the** entire treatment period. The theoretical dose intensity (TDI) (mg/cycle) is 3360 mg ((160mg/d x 21d ). The dose intensity (DI) actually received is equal to the total dose received divided by the total duration of treatment. The relative dose intensity (DIR) is equal to DI / DIT.

- **Time to deterioration in independence** is defined as the time from the date of inclusion to the date on which the IADL score (Appendix 2) has decreased by at least 1 point from the score calculated at inclusion. Patients alive or deceased without deterioration of autonomy will be censored at the date of last IADL assessment or the date of death.

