## **11.3 Calculation of the number of subjects required**

The clinical assumptions are based on data from the CORRECT study and are as follows:

$H_0$  : A tumor control rate at 2 months after the start of treatment of 25% or less is not sufficient

$H_1$  : A tumor control rate at 2 months after the start of treatment of more than 25% is considered sufficient. A rate of 47% is expected.

With a one-sided  $\alpha$  risk of 5% and 90% power, 42 patients are required.

Patients who discontinue the study prior to documented tumor progression at 2 months will be considered non-responders for the primary endpoint analysis.

The decision rules after inclusion of 42 patients are:

If 15 or fewer patients show a complete or partial response or stability, then the treatment will be considered not effective.

If 16 or more patients have a complete, partial or stable response, then the treatment is considered effective.

A recruitment of 2 patients per month is planned.

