1.4 Sample Size calculation

Clinical hypotheses are based on data from the CORRECT study and are as follows:

H₀: A tumor control rate at 2 months after the start of treatment of 25% or less is not sufficient.

H₁: A tumor control rate at 2 months after the start of treatment of more than 25% is considered sufficient. A rate of 47% is expected.

With a one-sided risk α of 5% and power of 90%, 42 patients are needed.

Patients who stop the study before documented tumor progression at 2 months will be considered non-responders for the primary endpoint analysis.

The decision rules after inclusion of 42 patients are:

- If 15 or fewer patients have a complete or partial response or stability then the treatment will be considered non-effective.
- If 16 or more patients have a complete or partial response or are stable, then the treatment will be considered effective.

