4.4.3 Objective response

4.4.3.1 Definition

It is defined as the percentage of patients in objective response, i.e., complete response (CR) or partial response (PR) as assessed by the investigator according to RECIST v1.1 criteria. The objective response will be determined from the best response during treatment assessments. Patients who discontinue treatment without response assessment will be considered as having no objective response.

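### The primary-endpoint population leaves out treated failures who have no on-treatment scan, and SAP 4.3.1 gives three groups of patients no stated outcome

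*SAP*

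**What the plan says.** **Population.** SAP 4.3 and 4.3.2 name ITTm for the primary endpoint. SAP 2.1.2 limits ITTm to patients with at least one tablet and at least one imaging assessment on protocol treatment. Protocol 11.4 asks only for one tablet. The table in SAP section 4 ticks ITT for the main criterion, and SAP 2.1.1 defines ITT as everyone included. Protocol 8.1 schedules scans every 8 weeks. SAP 4.3.2 allows the decision rule to be adjusted to the number of evaluable patients.

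**Outcomes fixed by SAP 4.3.1.** Failure is assigned to stops before 2 months for radiological progression or death, and to a missing 2-month scan with earlier progression or death. A further rule reads: "In case of clinical progression, if no imaging is available, the patient will be considered to have failed tumor control".

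**Outcomes left open by SAP 4.3.1.**
- Treatment stops for other reasons: "Discontinuations for other causes will be reviewed on a case-by-case basis; verify that the patient has not taken any subsequent treatment" before the imaging date.
- Clinical progression with imaging available: "otherwise, review the medical record to determine the reason for the clinical progression". This group is narrower than it looks, because a missing 2-month scan with progression recorded earlier is already a failure.
- No 2-month scan and no earlier progression or death: "If 2-month imaging is not available, subsequent imaging will be reviewed if available and the patient record will be reviewed".

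**Rules elsewhere.** SAP 4.4.2.1, for the same rate read centrally, fails every patient who stopped treatment before the 2-month assessment. SAP 1.4 says: "Patients who stop the study before documented tumor progression at 2 months will be considered non-responders for the primary endpoint analysis". Protocol 11.3 has the same rule. Protocol 11.1 asks for control while on regorafenib.

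**The concern.** The trial has one arm and its verdict rests on a single count. Two things must therefore be settled in advance: who is in the denominator, and how each patient in it is classified.

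On the first, three populations are named for one endpoint. The one that the analysis text uses excludes some of the patients whom the endpoint definition calls failures. The rule for clinical progression without imaging can hardly operate in a population that requires imaging.

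On the second, three groups receive an instruction to look but no result. SAP 3.3 offers no fallback, since missing data are not replaced unless specified. The investigator and central rates can then differ by rule as well as by reader, and in an open trial the gap would be filled by judgement after the data are known.

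**Working it through.** **Inputs.** Null rate 25%, expected rate 47%, one-sided 5% risk, 90% power, 42 patients, success at 16 or more (SAP 1.4, Protocol 11.3). SAP 4.3.2 prints 15 for both verdicts, so the cut-off of 16 is taken from the other two places. The documents give no number of patients without a scan and none for the review groups; d and k below are assumptions.

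**The plan's own figure.** With P(X ≥ c | n, p) = Σ C(n,x) pˣ(1−p)ⁿ⁻ˣ summed over x = c to n:
- P(X ≥ 16 | 42, 0.25) = 0.0416, the type I error
- P(X ≥ 16 | 42, 0.47) = 0.9057, the power

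The design is reproduced.

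**Effect on the confidence limit.** The exact one-sided 95% lower limit for x of n is the 5% quantile of Beta(x, n−x+1).
- 15/42 = 35.7%: lower limit 23.5%
- 16/42 = 38.1%: lower limit 25.6%
- 15/39 = 38.5%: lower limit 25.4%

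Removing three failures thus turns a result that SAP 1.4 calls not effective into one whose lower limit exceeds 25%.

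**Effect on type I error, cut-off re-derived.** Let d of 42 treated patients be failures without imaging. If control in all 42 is 25% (10.5 expected), the rate in the remaining 42−d is q = 10.5/(42−d). The cut-off c is the smallest with P(X ≥ c | 42−d, 0.25) ≤ 0.05.

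| d | n | c | q | P(X ≥ c given n, q) |
|---|---|---|---|---|
| 1 | 41 | 16 | 0.2561 | 4.1% |
| 2 | 40 | 16 | 0.2625 | 4.0% |
| 3 | 39 | 15 | 0.2692 | 7.8% |
| 6 | 36 | 14 | 0.2917 | 13.6% |

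**Effect on type I error, 42 evaluable patients obtained and 16 kept.** Two models for the dropped patients:
- d extra treated patients, q = 0.25(42+d)/42: 5.1%, 6.1%, 7.3% and 11.8% for d = 1, 2, 3, 6
- a dropped share of d/42, q = 0.25/(1−d/42): 5.1%, 6.2%, 7.6% and 13.6%

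**Effect of the open outcomes.** If the scan decides and control is defined by it, type I error stays at 4.2%. If k unresolved patients, taken at random, are all called controlled, success needs 16−k among the other 42−k:
- k = 1: P(X ≥ 15 | 41, 0.25) = 6.7%
- k = 2: P(X ≥ 14 | 40, 0.25) = 10.3%
- k = 3: P(X ≥ 13 | 39, 0.25) = 15.4%

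**The case against.** A reader might infer that SAP 4.3.1 flatly contradicts SAP 1.4 and Protocol 11.3. The documents do not establish this. Those two places speak of leaving the study. Protocol 7.1 and 8.2 keep patients who stop treatment before progression in follow-up, with scans every 8 weeks. The wording does drift. For objective response, Protocol 11.1 says "Patients who discontinue the study without response assessment will be considered non-responders", while SAP 4.4.3.1 says "Patients who discontinue treatment without response assessment will be considered as having no objective response". That makes the reach of SAP 1.4 unclear; it does not prove a conflict.

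Nor is the first review group wholly without guidance. Checking that no other treatment came before the imaging makes sense only if the scan then decides, which points to a scan-based outcome. What is missing is the statement of it.

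A reader might also suppose that review could turn the fixed failures into successes. SAP 4.3.1 does not send those patients to review, so error rates built on that assumption do not apply.

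The median treatment duration of 7.1 weeks in patients over 65 (Protocol 1.2) covers stops for every reason. It shows that stops near the first scan will be common, not how many fall in the review groups.

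On the population, some patients may be scanned before week 8, as SAP 4.3.1 itself foresees, and one or two dropped patients cause no inflation when the cut-off is re-derived. Both points limit the size. Neither answers the mismatch between ITTm, Protocol 11.4 and the SAP table.

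**Conclusion.** The population fault stands as written. ITTm removes treated patients whom SAP 4.3.1 counts as failures, and it disagrees with Protocol 11.4 and with the SAP's own table. The direction is certain: dropping failures can only raise the rate. The size depends on the unknown number dropped. It is negligible for one or two patients with a re-derived cut-off, and about 7% to 8% type I error for three and 12% to 14% for six, against 4.2% planned.

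The missing outcomes in SAP 4.3.1 and the different rule in SAP 4.4.2.1 also stand. Their size is unknown: none if the scan decides, and 6.7% to 15.4% only if one to three unresolved patients are all called controlled. Whether SAP 1.4 and Protocol 11.3 cover treatment stoppers has to be reconciled. The documents do not settle whether every early stop should be a failure or the scan should decide.

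**What to change.** 1. Analyse the primary endpoint in all included patients who took at least one tablet (Protocol 11.4), and count those without on-treatment imaging as failures. Correct SAP 4.3, 4.3.2 and the section 4 table to match. With 42 treated patients the cut-off of 16 stands (type I error 4.2%, power 90.6%).
2. Before database freeze, as SAP 1.6 requires, replace the case-by-case and record reviews in SAP 4.3.1 with one stated outcome per group. Use the same rule in SAP 4.4.2.1, and reconcile it with SAP 1.4 and Protocol 11.1 and 11.3.
3. Count a patient with no evaluable 2-month scan as a failure unless a later scan, with no new anticancer treatment before it, shows complete response, partial response or stable disease. State which rule takes precedence for a patient who stops before week 8 and is scanned only afterwards.
4. Report the handling of early stoppers that is not chosen (all failures, or scan-based with no new anticancer treatment) as a labelled sensitivity analysis for both readings.

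The cost is SAP wording, with no change in sample size. The observed rate may be lower. For illustration, if the true rate fell from 47% to 45% or 42% (assumed), power at 16/42 would be 85.4% or 74.7%.

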4.3.2 Evaluation

The primary endpoint will be assessed on the ITTm population. This criterion will be described according to the usual descriptive statistics. A one-sided 95% confidence interval will be calculated using the exact method.

The decision rules to be applied on 42 patients evaluable during the analysis (ITTm population) are :

- If 15 or less patients have a complete or partial response or stability, then the treatment is judged not effective.
- If 15 or more patients have a complete or partial response or are stable, then the treatment is considered effective.

These may be adjusted based on the actual number of evaluable patients included.

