## **11.4 Statistical analysis**

### **Populations of analysis**

All analyses will be done on an intention-to-treat basis on all included patients who have taken at least one treatment tablet.

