2.1.2 Modified Intent-to-treat population (ITT_m)

The modified intention-to-treat population is defined as all patients included in the study who received at least one regorafenib tablet and had at least one imaging assessment under protocol treatment.

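### The SAP's primary tumour control analysis requires an on-treatment scan, so treated patients who die, progress clinically or stop unscanned are dropped instead of counted as failures

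*SAP*

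**What the plan says.** The SAP names the modified intention-to-treat population (ITTm) for the primary endpoint in the heading of 4.3 ("Population : ITTm") and again in 4.3.2 ("The primary endpoint will be assessed on the ITTm population"). It then ties the decision rule to 42 evaluable ITTm patients and allows that rule to be adjusted to the number actually evaluable, without giving a method. SAP 2.1.2 limits ITTm to included patients who "received at least one regorafenib tablet and had at least one imaging assessment under protocol treatment".

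Other current text points elsewhere:

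- **Protocol 11.4:** "All analyses will be done on an intention-to-treat basis on all included patients who have taken at least one treatment tablet". There is no scan condition.
- **Protocol 11.3:** "Patients who discontinue the study prior to documented tumor progression at 2 months will be considered non-responders for the primary endpoint analysis".
- **SAP 1.4** repeats this: "Patients who stop the study before documented tumor progression at 2 months will be considered non-responders for the primary endpoint analysis".
- **SAP section 4 table:** under "Main criterion", tumour control is marked in the ITT column.
- **SAP 4.3.1:** "In case of clinical progression, if no imaging is available, the patient will be considered to have failed tumor control". It also treats stopping because of death before 2 months as failure.

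**The concern.** Entry to ITTm depends on something that happens after treatment starts and is closely tied to outcome. Protocol 8.1 schedules the first tumour scan at 8 weeks, essentially the time of the endpoint. A patient who dies or deteriorates before then may never be scanned on treatment, and so is removed from the analysis rather than counted against the drug.

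The SAP 4.3.1 rules do not repair this. The rules for clinical progression without imaging and for stopping because of death cannot act on a patient with no scan at all, because that patient is not in the population. The separate rule for patients who die after an earlier scan still works.

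At stake are the reported control rate, its one-sided lower confidence limit and the verdict on efficacy. Because the rule may be adjusted by an unstated method, the denominator and cut-off could also be settled after outcomes are known in an open-label, single-arm trial.

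**Working it through.** **Inputs.** Null rate 25%, expected rate 47%, one-sided alpha 5%, power 90%, 42 patients, success at 16 or more (Protocol 11.3, SAP 1.4). The one-sided 95% exact limit is from SAP 4.3.2. Two quantities are not in the documents and are assumed: e, the share of treated patients with no on-treatment scan (5% to 20%), and q, the share of those patients who are in fact controlled (0, then 10% and 20%).

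**The plan's own figure.** By the exact binomial, P(X ≥ 16 | 42, 0.25) = 0.0416 and P(X ≥ 16 | 42, 0.47) = 0.906. The stated design is reproduced.

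**Rate within ITTm.** If the true rate in all treated patients is 25%, the rate among the scanned is r = (0.25 − e·q)/(1 − e). With q = 0 this is 0.25/(1 − e): 26.3%, 27.8%, 29.4% and 31.3% for e = 5%, 10%, 15% and 20%. At e = 0 there is no bias.

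**Chance of declaring efficacy when the true all-treated rate is 25%:**

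| Scenario | e = 5% | 10% | 15% | 20% |
|---|---|---|---|---|
| (1) 42 ITTm patients, cut-off 16, q = 0 | 6.3% | 9.6% | 14.4% | 21.2% |
| (1) with q = 10% | 5.4% | 7.0% | 9.3% | 12.3% |
| (2) 42 treated, cut-off re-derived, q = 0 | 5.3% | 8.1% | 11.9% | 16.7% |
| (2) with q = 10% | 4.5% | 5.9% | 7.8% | 9.9% |
| (3) 42 treated, cut-off kept at 16, q = 0 | 4.2% | 4.2% | 4.2% | 4.2% |

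- Scenario (1) is P(X ≥ 16 | 42, r).
- Scenario (2) draws the number unscanned from Binomial(42, e) and, for each remaining n, uses the smallest cut-off with exact alpha of at most 5% at 25%.
- Scenario (3) loses nothing when q = 0, because only failures are removed and the count needed is unchanged.
- The probability that the Clopper-Pearson one-sided 95% lower limit on ITTm exceeds 25%, computed separately, equals scenario (2). Even in (3), the reported limit clears 25% that often.

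**A case where the verdict changes.** Take 15 controlled patients among 42 treated.

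- All treated: 15/42 = 35.7%, lower limit 23.5%, cut-off 16. Not effective.
- Three never scanned: 15/39 = 38.5%, lower limit 25.4%, exact cut-off for 39 patients is 15. Effective.

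The exact cut-off is still 16 for n = 40 and 41 (15/40 has lower limit 24.7%), so three lost patients are the smallest number that changes this decision.

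**The case against.** The strongest reply is that the SAP contains the right rules and that the harm depends on how it is read. Its table says ITT, SAP 1.4 makes early leavers non-responders, and 4.3.1 fails patients with clinical progression and no imaging. This is true, but it shows a contradiction. The section that governs the primary analysis, and its decision rule, say ITTm, and that label disables the failure rules for patients never scanned.

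Five points on size and detail deserve weight:

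- **Scenario (1) needs more than 42 inclusions** if anyone is unscanned. Protocol 11.3 and SAP 1.4 set the rule after 42 inclusions, and no replacement is described. Still, SAP 4.3.2 does specify 42 ITTm patients.
- **The cut-off of 16 comes from Protocol 11.3 and SAP 1.4.** SAP 4.3.2 puts 15 in both the effective and the not-effective outcome. That is a separate error; a cut-off of 15 of 42 would have alpha 8.1% even without exclusions.
- **Adjustment is optional.** If 16 is kept with 42 treated, the test is protected.
- **Some unscanned patients may be controlled.** Protocol 8.2 continues scans after stopping for reasons other than progression, and ITTm leaves out such a patient if no scan was done on treatment. At q = 20%, scenario (2) gives 3.8%, 4.3%, 4.8% and 5.2%, so inflation largely disappears.
- **The sources for the right population differ.** SAP 2.1.1 defines ITT as all included patients; Protocol 11.4 requires one tablet. Neither requires a scan.

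These points limit the certainty about size. They do not remove the conflict or the direction of the bias when unscanned patients are mostly failures.

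**Conclusion.** The concern holds. As written, SAP 4.3 and 4.3.2 contradict the Protocol's analysis population, the non-responder rule in both documents and the SAP's own table, and they exclude patients on a criterion linked to failure. This must be corrected, because it affects the primary endpoint and the decision rule.

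Confidence in the contradiction is high. The size is conditional on e and q, which the documents do not give. The Protocol's background section reports a median treatment duration of 7.1 weeks in patients over 65 in the cited phase III trial. This makes stopping near the first scan plausible, but it is not an estimate of e: on a 21-days-on, 7-days-off schedule, second-cycle dosing ends at day 28 + 21 = 49, or 7.0 weeks.

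**What to change.** In SAP 4.3 and 4.3.2, replace ITTm with all included patients who took at least one tablet. This is the Protocol 11.4 population and already exists as the SAP safety population (2.1.3). Then:

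- Count as failures those who die, progress clinically or discontinue with no tumour assessment, in line with Protocol 11.3 and SAP 1.4.
- Keep the 4.3.1 review of later imaging for patients still on study who missed the 2-month scan, and count them as failures if no later imaging exists. A 2-month scan done after stopping treatment is a tumour assessment and stays under the 4.3.1 review.
- Apply the 16-of-42 rule and the one-sided exact limit to this denominator, and remove the open-ended adjustment to evaluable patients. If slightly fewer than 42 are treated, keeping 16 is conservative: alpha is 3.3% at 41 and 2.6% at 40.
- Align the section 4 table with the text, and correct the overlapping 15 in 4.3.2 at the same time.
- Keep ITTm only as a labelled sensitivity analysis.

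The cost is SAP wording, which SAP 1.6 permits before database freeze. No new data are needed. The reported rate may be somewhat lower.

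### SAP 4.3.2 classes 15 controlled patients out of 42 as both effective and not effective; a cut-off of 15 carries an 8.05% one-sided error, not 5%

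*SAP*

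**What the plan says.** The design assumptions are the same in Protocol 11.3 and SAP 1.4. The null is "A tumor control rate at 2 months after the start of treatment of 25% or less is not sufficient"; for the alternative, "A rate of 47% is expected". The error rates and size follow: "With a one-sided risk α of 5% and power of 90%, 42 patients are needed".

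The decision rule is stated three times:

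- **Protocol 11.3:** 15 or fewer is not effective; "If 16 or more patients have a complete, partial or stable response, then the treatment is considered effective".
- **SAP 1.4:** 15 or fewer is not effective; "If 16 or more patients have a complete or partial response or are stable, then the treatment will be considered effective".
- **SAP 4.3.2** (the section that governs the primary analysis): "If 15 or less patients have a complete or partial response or stability, then the treatment is judged not effective", followed by "If 15 or more patients have a complete or partial response or are stable, then the treatment is considered effective".

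SAP 4.3.2 then adds "These may be adjusted based on the actual number of evaluable patients included". It also asks for an exact one-sided 95% confidence interval for the control rate.

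**The concern.** The first two statements split the possible counts cleanly between 15 and 16. The third overlaps at 15, so under SAP 4.3.2 a result of 15/42 supports either conclusion. Nothing in the SAP says that section 1.4 takes precedence over section 4.3.2.

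This is the study's only pre-specified rule for declaring success or failure. If 15/42 were observed, the conclusion would be chosen after the result was known, and the favourable choice would exceed the stated 5% error. The open adjustment sentence adds to this. The rule is applied to patients with at least one tablet and at least one on-treatment imaging assessment (SAP 2.1.2), so the denominator may not be 42, and no method is given for moving the cut-off.

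**Working it through.** **Inputs** (SAP 1.4 and Protocol 11.3): null rate p0 = 0.25, expected rate p1 = 0.47, one-sided alpha 0.05, power 0.90, n = 42.

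**Formula.** With X controlled patients out of n, P(X ≥ r | n, p) = Σ C(n,k) p^k (1−p)^(n−k), summed over k = r to n. Setting p = p0 gives the type I error; setting p = p1 gives the power.

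**Step 1: reproduce the sample size.** For each n, take the smallest r with P(X ≥ r | n, 0.25) ≤ 0.05, then compute the power at 0.47. The smallest n with power of at least 0.90 is 42, with r = 16. The plan's figure of 42 therefore reproduces as an exact binomial design, and its cut-off is 16.

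**Step 2: compare the two cut-offs at n = 42.**

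| Success at | Error at 25% | Power at 47% | Exact one-sided 95% lower limit at the cut-off |
|---|---|---|---|
| 15 or more | 8.05% | 94.9% | 23.5% (15/42 = 35.7%) |
| 16 or more | 4.16% | 90.6% | 25.6% (16/42 = 38.1%) |

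The lower limit is the Clopper-Pearson limit, i.e. the 5% quantile of a Beta(x, n − x + 1) distribution. The two error rates differ by P(X = 15 | 42, 0.25) = 3.89%, and 8.05% − 3.89% = 4.16%. The ratio is 8.05/4.16 = 1.9; against the nominal 5% it is 8.05/5 = 1.6.

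**Step 3: how likely is a count of exactly 15?** The documents do not give the true rate, so a range is shown.

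| True control rate | P(X = 15), n = 42 |
|---|---|
| 25% | 3.9% |
| 35% | 12.7% |
| 40% | 10.8% |
| 47% | 4.3% |

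**Step 4: other numbers evaluable.** Leaving the cut-off at 16 gives an error of 5.1% at n = 43 and 6.3% at n = 44, so an adjustment is needed above 42. The smallest r with exact error of at most 5% is:

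| n evaluable | Cut-off r | Error at 25% | Power at 47% |
|---|---|---|---|
| 37 | 15 | 2.7% | 82.9% |
| 38 | 15 | 3.5% | 86.3% |
| 39 | 15 | 4.4% | 89.1% |
| 40 | 16 | 2.6% | 85.2% |
| 41 | 16 | 3.3% | 88.1% |
| 42 | 16 | 4.2% | 90.6% |
| 43 | 17 | 2.5% | 87.2% |
| 44 | 17 | 3.2% | 89.7% |
| 45 | 17 | 3.9% | 91.8% |
| 46 | 17 | 4.8% | 93.6% |

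In every row the exact one-sided 95% lower limit is above 25% at r and below 25% at r − 1, so this rule and the interval in SAP 4.3.2 cannot disagree.

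**The case against.** The strongest reply is that this is a one-digit slip. Of the six rule statements (two each in Protocol 11.3, SAP 1.4 and SAP 4.3.2), five are consistent with success starting at 16. A careful reader would infer 16, and then the error is 4.16% and the design is sound. That is probably how the line arose, and the 8.05% is indeed conditional on reading 15/42 as success. It does not remove the point, because the odd statement sits in the section the analyst will apply.

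It can also be said that the SAP never makes the confidence interval a decision criterion. That is correct. The conflict is that a success declared at 15/42 would be reported beside a lower limit that does not exclude 25%; no stated interval rule is broken.

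On the adjustment sentence, the null rate and alpha are already fixed, which largely determines a sensible recalculation, and SAP 1.6 requires changes to the plan before database freeze. Both points limit the problem. But the method is not written down, and the study is open-label, so a deadline at freeze does not ensure that the cut-off is set without knowledge of the count.

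Finally, a rule that controls alpha alone gives less than 90% power at several sizes, for example 85.2% at n = 40. That is true, but it follows from the number evaluable and the 5% limit, not from writing the rule down.

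**Conclusion.** The concern holds: SAP 4.3.2 is wrong as written. At 15/42 it gives two opposite conclusions, and its threshold of 15 has an exact one-sided error of 8.05% against the stated 5%. The threshold of 16 in Protocol 11.3 and SAP 1.4 reproduces the design, with error 4.16% and power 90.6%.

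The figures assume exactly 42 patients in the denominator and true rates of 25% and 47%. The 8.05% applies only if 15/42 is resolved as success. The missing adjustment method is a secondary point. The correction must be made before the primary analysis because it concerns the primary decision threshold.

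**What to change.** 1. In SAP 4.3.2, change the success line from 15 or more to 16 or more, to match Protocol 11.3 and SAP 1.4.
2. Replace the open adjustment sentence with a fixed rule: for n patients in the primary analysis, the treatment is considered effective if the count reaches the smallest r with exact P(X ≥ r | n, 0.25) ≤ 5%. This gives 15 for n = 37–39, 16 for n = 40–42 and 17 for n = 43–46, and is equivalent to requiring the exact one-sided 95% lower limit to exceed 25%. State that power at 47% may fall below 90% when n is not 42.

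The cost is two lines of SAP text, with no new data and no change in sample size. To apply the second item, the SAP must also settle which patients make up n: sections 4.3 and 4.3.2 name the modified intention-to-treat population, the table in section 4 marks the main criterion under intention-to-treat, and Protocol 11.4 analyses all included patients who took at least one tablet.
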